3.7 Recruitment

Based on the volume of immobilized patients transported in each of the 12 new proposed participating centers, we expect there could be 8,129 eligible cases over the proposed 12-month evaluative period (required sample size is 7,200). We are confident that the required sample size can be obtained with the participation of the proposed centers, and we have accounted for unlikely attrition in our study design and sample size calculation.

We also plan to employ a number of strategies during the enrollment phase of the study in order to meet our recruitment goals. We have specifically approached Ontario EMS Services that have previously and successfully participated in prehospital research. These paramedics will be familiar with completing specific study paperwork. We will be approaching the vendors of the software used by EMS Services in order to develop a study form that is easy to access, complete and submit. We will employ a local study champion at each EMS Service who will be accessible to the front-line paramedics to answer questions, deliver updates and reminders and provide feedback regarding certain cases or applications of the CCR.

Lastly, we will develop a study website, and utilize social media to keep the participating EMS Services and their staff engaged in the study.

Section 4: Methods: Assignment of Interventions

The 12 new participating EMS Services will be randomized using the technique of covariate constrained allocation to protect against chance imbalances in the following prognostic factors: catchment area (km²), number of immobilizations per month, average response time and staff make-up (advanced care paramedics and primary care paramedics) . Due to the relatively small number of allocation units, it is particularly important to use an allocation technique that minimizes the risk of chance imbalances. In the stepped-wedge design, randomization is with respect to the timing of implementation of the intervention. Effective randomization is essential to protect the internal validity of the trial, including the ability to obtain a valid estimate of any secular trend, as well as a valid estimate of the intervention effect. Covariate constrained allocation was selected as it was found to be superior to simple stratification and matching in a recent simulation study (16). In covariate constrained allocation, all possible allocations of sites will be considered (a total of 34,650 possible allocations), and those that are acceptable – in that they meet a set of balance constraints – will be identified. One of the allocations will then be randomly selected from among the set of acceptable allocations. To protect the validity of the randomization, the number of times that any given pair of sites receives the same allocation will be counted and constraints will be relaxaed if the design is found to be overly constrained. The allocation will be performed using a SAS macro developed for this purpose, by an independent statistician not associated with the trial. Allocations will be securely kept by the independent statistician and will be concealed from the study investigators and all participating sites, until one month before the allocated start time of a particular site.

Section 5: Methods: Data Collection, Management, and Analysis

5.1 Data Collection Methods

Once training of paramedic staff has been completed, paramedics will begin evaluating eligible patients with the CCR. Each time an eligible patient is assessed using the CCR, the paramedic treating that patient will complete and submit an electronic CCR (see Appendix 6. Paramedic Data Collection Form). The paramedic will also record patient-reported comfort level and pain level on this form. Staff at the study coordinating centre will receive the electronic EMS-completed CCR, as well as a copy of the Paramedic Care Record (ePCR). Study staff will review the paramedic documentation in order to assess compliance with the study protocol and application of the CCR. Information on patient age, gender, mechanism of injury, field time, offload time and immobilization status are contained in the ePCR and will be recorded from there (see Appendix 7. Study Data Collection Form).

We will link the information obtained from paramedic care records to provincial administrative databases housed at ICES. This linkage will allow us to obtain information related to the initial ED visit, c-spine diagnostic imaging, hospitalization, and subsequent ED/clinic/family physician visits within 30 days of injury.

5.2 Data Collection Methods - Retention

We will employ a number of methods to minimize the number of missed cases and amount of missing information on EMS-completed data forms. We will work closely with local Study Champions to ensure that there are regular study updates, visible study advertisements and electronic reminders. Paramedics

will be able to connect with their local study champion, or remotely with study staff via e-mail, website communication or social media. We will provide feedback to services on aspects of the study that are going well, as well as areas where improvement may be needed. We will provide regular progress reports to participating sites, as well as Base Hospitals. Ultimately though, this study has been designed as a pragmatic trial. We will do our utmost to keep the study at the forefront using the methods described above, but we will not have the time nor the resources to locate and follow-up on missed cases (i.e. those cases where the CCR was not used but should have been).

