2.3 Trial Design

The multicentre implementation of the CCR by paramedics is designed as a stepped wedge cluster randomized trial with three steps, involving a total of 13 Ontario EMS Services. Our 36-month study will consist of a 12-month set-up and training period (Year 1), followed by the stepped wedge trial (Year 2), and a 12-month period for study completion, analyses, and knowledge translation and exchange (see Figure 2). EMS services in each step will cross from the control condition (usual care) to the intervention condition (CCR implementation) at intervals of 3 months until all communities have crossed to the intervention. Data will be collected on all eligible patients in each EMS service for a total duration of 12 months.

Figure 2: Diagram of the Study and Stepped Wedge Design

-8			Months 1-9		Months 10-12	
ar 1		Study set-up	Paramedic			
Year		ePlatform progra	ePlatform programming for EMS data collection			
		Preparation of study material and site visits				
	Step	Months 1-3	Months 4-6	Months 7-9	Months 10-12	
ır 2	1 (4 EMS services)	Usual Care	CCR	CCR	CCR	
Year	2 (4 EMS services)	Usual Care	Usual Care	CCR	CCR	
	3 (4 EMS services)	Usual Care	Usual Care	Usual Care	CCR	
		Months 1-6		Months 7-9	Months 10-12	
ar 3		Study completion		Data cleaning	Reports and	
Year		Data linkage with ICES		Data analyses	manuscripts	
					writing; KTE	

Section 3. Methods: Participants, Interventions and Outcomes

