3.2 Eligibility Criteria

All consecutive, alert (able to follow commands), stable patients (normal vital signs) evaluated by the paramedics employed by a participating EMS Service for potential cervical spine injury after sustaining acute blunt trauma (within 48 hours). These are patients for whom standard Ontario EMS trauma protocols usually require immobilization. As in prior CCR studies, patients will be excluded if they do not require immobilization as per the standard Ontario EMS trauma protocol, have a Glasgow Coma Scale score less than 15 or are intubated, or have unstable vital signs (systolic blood pressure < 90 mmHG; respiratory rate <10 or >24 breaths/minute). Patients will also be excluded if: their injury occurred more than 48 hours previously; they have penetrating trauma from stabbing or gunshot wound to the neck, acute paralysis, or known vertebral disease (specifically ankylosing spondylitis, rheumatoid arthritis, spinal stenosis or previous cervical spine surgery); they were referred from another hospital and transported between facilities; or they are younger than 8 years.

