3.3 Interventions

Paramedics will be trained in the use of the CCR prior to the start of the trial. We have conducted an Ottawa EMS CCR implementation pilot study and have designed our training program to address barriers identified in the pilot. The training entails one hour of education: 30 minutes of self-review of a teaching video addressing the background and scientific development of the CCR, and a 30-minute inclass teaching video reviewing the specific steps involved in using the CCR, complete with a demonstration and question and answer period with a certified trainer. Paramedics will be "certified" to clear the cervical spine by medical directive if they have: a) successfully completed the initial training sessions, and b) successfully completed (score of ≥80%) a written quiz. Paramedics failing the written quiz would be required to attend a remedial session and review all wrong answers with their certified trainer. Of note, Ottawa paramedics all successfully completed their training.

The stepped wedge trial will begin after paramedic training has been completed (see Figure 2). During the Usual Care phase, paramedics will complete the CCR data collection form for all eligible patients, but will continue to immobilize them all before transport to the receiving hospital. Once a community has crossed to the intervention CCR phase, paramedics will be permitted by medical directive to implement the CCR. Paramedics will then transport selected patients without immobilization according to the CCR. Although following the medical directive will be mandatory for paramedics, they will be encouraged and allowed to immobilize patients if they are uncomfortable with the CCR's recommendation to not immobilize them.

During the study set-up time period (Figure 2), each participating service will designate a local paramedic study champion. These individuals will be in close contact with staff at the Study Coordinating Centre and will receive further information about the study, the methodology and the implementation of the CCR. These individuals will be heavily involved in delivering the study training material at their particular location and will serve as a first point of contact throughout the implementation. Paramedics with questions about specific aspects of the CCR, or the application of the CCR for unusual scenarios will be able to communicate directly with a peer in an effort to promote adherence to the protocol.

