7.3 Consent

We will be seeking a waiver of informed consent from the OHSN-REB. This was the case in the previous multi-centre prehospital validation of the CCR, as well as the single-centre prehospital implementation study. The study protocol has been reviewed by the Medical Advisory Committee for the Ontario Base

Hospitals Group (MAC – OBHG). The MAC provides advice to the Emergency Health Services Branch (EHSB) of the Ontario Ministry of Health and Long-Term Care. Paramedics employed by EMS Services participating in the study will be allowed via a Medical Directive to use the CCR to evaluate eligible patients instead of the usual immobilization protocols. The Medical Directive will be drafted by the MAC-OBHG and authorized by the EHSB for the duration of the study.

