7.4 Confidentiality

Paramedics will evaluate eligible patients using the CCR. They will complete an electronic form that will capture information on the elements of the CCR, as well as pain, patient comfort, and paramedic comfort with using the CCR. The electronic form will not include any information that can identify a patient. Upon receipt of the electronic form, study staff will assign a unique study number. We will also receive the corresponding paramedic documentation electronically that will allow us to capture the remainder of the pre-hospital data required. The paramedic documentation will also be transmitted electronically, stripped of patient identifiers.

In order to link the pre-hospital information with the data housed at ICES, we will need to maintain a list of eligible enrolled patients, including first name, last name, date of birth, sex, postal code, health card number (where available). This list will be generated and maintained by staff at each Base Hospital, or EMS Service if Base Hospital staff are unable to access this information. The information will be stored in a password-protected, encrypted spreadsheet. When this information is required by ICES for linkage purposes, it will be transmitted securely according to their protocols. The linked information that we receive back from ICES will be stripped of personal identifiers before we receive it. All paper study files will be stored in locked filing cabinets in a locked office. All electronic files will be stored on limited-access network folders which are backed up regularly. Any information shared with DSMB Members or other study committees will not include any identifiable information.

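### The primary reduction will describe patients with a submitted CCR form, not all eligible patients, and section 5.4 plans no analysis to bridge the two

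*Combined protocol and SAP*

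**What the plan says.** The stated target is complete coverage. Section 2.3 says "Data will be collected on all eligible patients in each EMS service for a total duration of 12 months", and section 3.2 speaks of consecutive patients.

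The data flow is narrower. Section 5.1 says "Each time an eligible patient is assessed using the CCR, the paramedic treating that patient will complete and submit an electronic CCR", and the coordinating centre receives the paramedic care record alongside that form. Section 7.4 adds "Upon receipt of the electronic form, study staff will assign a unique study number". For missed cases, defined as "those cases where the CCR was not used but should have been", section 5.2 says "we will not have the time nor the resources to locate and follow-up on missed cases".

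On the care such patients would receive, section 3.2 says of the eligible group "These are patients for whom standard Ontario EMS trauma protocols usually require immobilization". Under section 7.3, paramedics in participating services "will be allowed via a Medical Directive to use the CCR to evaluate eligible patients instead of the usual immobilization protocols". Section 3.3 says that "following the medical directive will be mandatory for paramedics", while letting them immobilize a patient when they are uneasy with the rule's advice.

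Section 5.4 fits a mixed model to individual patient records. It names no analysis population and plans no estimate for all eligible patients. Its only stated sensitivity analyses belong to the economic evaluation (complete cases, and the cost of the intervention). It also announces an Ontario budget impact analysis.

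**The concern.** A missed case is defined by the intervention not being used. In an implementation trial, eligible patients in whom the rule was never applied are part of the question, yet they leave both numerator and denominator. The recorded reduction is then partly conditional on having received the intervention.

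Loss acts mainly through the CCR phase. In usual care everyone is to be immobilized, so a missing form hardly changes the control proportion. In the CCR phase, a patient without a form has probably been handled under the usual protocol, that is, immobilized. Leaving such patients out makes the reduction look larger than it is among all eligible patients.

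What is at stake is the size of the effect and its extension to the province. Section 2.2 already frames the expected benefit in terms of all eligible Ontario trauma patients, and the budget impact analysis will need a number of immobilizations avoided.

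**Working it through.** **The plan's own figure.** Section 3.6 gives more than 99.9% power for a 10-point reduction from 100% immobilized, with 12 services, 4 intervals, 150 patients per service-interval, an intracluster correlation of 0.05 and two-sided 2.5%. The Hussey-Hughes stepped-wedge variance gives a standard error of 0.0092 to 0.0133, depending on the variance assumed. At the largest, 0.10/0.0133 − 2.24 = 5.28, so power exceeds 99.99% and the figure reproduces. If only half the patients in each interval were captured and the effect were unchanged, primary power would still be 99.94%. Precision is not the issue.

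**Inputs for the effect size.**
- Observed reduction among patients with a form: 60 points, the pilot's approximate share of immobilizations avoided (section 2.1).
- *m*, share of eligible patients without a form, taken as equal in both phases: not given; assumed 5%, 10%, 20%.
- *q*, share of missed CCR-phase patients not immobilized: not given; assumed 0 to 100%.
- *q0*, the same share among missed usual-care patients: base case 0, in line with the 100% control proportion in sections 3.6 and 5.4.

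**Formula.** In each phase, the proportion not immobilized among all eligible patients is (1 − m) × the recorded proportion + m × the proportion among missed patients. Subtracting usual care from the CCR phase gives

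all-eligible reduction = (1 − m) × observed + m × (q − q0).

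**Results in points, q0 = 0, observed 60.**

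| m | q = 0 | q = 30% | q = 60% | q = 100% |
|---|---|---|---|---|
| 5% | 57.0 | 58.5 | 60.0 | 62.0 |
| 10% | 54.0 | 57.0 | 60.0 | 64.0 |
| 20% | 48.0 | 54.0 | 60.0 | 68.0 |

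Example: m = 20%, q = 30% gives 0.8 × 60 + 0.2 × 30 = 54.0. There is no bias when q − q0 equals the observed reduction; above that the direction reverses.

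**Dependence on q0.** With q = 0 and q0 = 10%, the values are 57.0 − 0.5 = 56.5, 54.0 − 1.0 = 53.0 and 48.0 − 2.0 = 46.0. So q = 0 gives a lower bound for a stated m only if q0 = 0.

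**The 10-point difference.** With q = q0 = 0, an observed 60 falls to 10 when 1 − m = 10/60, that is, m = 83.3%. At an observed reduction of exactly 10, the same assumption gives 9.5, 9.0 and 8.0 points at m = 5%, 10% and 20%. The reassurance therefore belongs to effects near the pilot's.

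**Check under the design.** In simulated stepped-wedge data (12 services, 4 quarters, service and quarter effects, 300 runs, q0 = 0, m and q constant and known), the formula matched the all-eligible estimate within 0.1 point for (m, q) = (10%, 0), (20%, 30%) and (20%, 100%). This confirms the algebra. It says nothing about the true m or q.

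**The case against.** The limit is disclosed and deliberate: section 5.2 gives pragmatic reasons and pairs them with champions, reminders, feedback and progress reports. With the mandatory directive, these should keep *m* down. A paramedic who completes the form but chooses to immobilize stays in the data (Appendix 6, question 4 after the rule), so overrides already count against the intervention. All of this stands, but it concerns how large the loss is. It does not settle what the estimate means once loss has occurred.

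A reader might infer that the protocol makes the form the sole route to a record. It does not say so. That is an inference from sections 5.1, 5.2 and 7.4, none of which describes another route. Section 5.3 plans work to locate missing data, which might recover a patient who was assessed but whose form went astray. Section 7.4 does not say how the linkage list of enrolled patients is built.

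It is also fair that section 2.2 is a planning statement and that section 5.4 gives no budget-impact method, so how the primary reduction would enter is not known. Finally, the formula only varies unobserved shares and produces no new evidence. Its value is that the range is fixed in advance and the limit stated beside the result.

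**Conclusion.** The point holds as a matter of whom the effect describes and how large it is. The primary reduction will apply to patients with a submitted form. Overstatement of the all-eligible reduction is the likely direction, because the default for a patient in whom the rule is not used is immobilization, but it is not certain. Under the assumed missed shares and q0 = 0, an observed 60 means 57, 54 or 48 points if all missed patients are immobilized, and 60 if 60% of missed CCR-phase patients are not. If the number of immobilizations avoided is scaled by the reduction, it would be 5%, 10% or 20% lower in the first case.

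Three stronger readings are not supported:
- That the primary test is compromised. Neither the test against no effect nor the 10-point difference is threatened at an effect near 60.
- That 7,200 over 8,129 (section 3.7) measures capture. The first is a required sample size and the second a projection; neither counts forms received.
- That a denominator already exists. Sections 3.7 and 4 draw on volumes of immobilized patients and immobilizations per month, which are not shown to be quarterly counts of eligible patients.

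This is worth correcting before analysis: the remedy is cheap and changes what can be concluded.

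**What to change.** 1. In 5.2 and 5.4, define the primary analysis population as patients with a submitted CCR form and limit the primary effect size to them. Say how a form filed for a patient later judged ineligible is handled; section 6.3 counts this as a protocol deviation.
2. Pre-specify a sensitivity analysis reporting (1 − m) × observed + m × (q − q0), for equal *m* in both phases, over stated ranges of *m*, *q* and *q0*, with q0 = 0 as base case. Call q = 0 a lower bound only under q0 = 0. Carry the same range into the budget impact analysis.
3. Report recorded enrolment by service, quarter and phase, beside the planning volumes where available, as a crude check for a change in capture at crossover. State that it cannot separate missed forms from seasonality or projection error.
4. Optional: where a service can readily produce it, a count from care records of immobilized trauma transports without a form, as a loose guide to *m*, since not all ineligible transports can be filtered out.

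Items 1 to 3 need no new patient data: some text, one formula-based table and one table of 12 services by 4 quarters. Item 4 needs new queries, which the resource limit in 5.2 may not allow. The downside is a little more analysis and a less favourable secondary figure. The comfort outcome cannot be recovered for patients without a form.

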5.3 Data Management

Data will be entered centrally at the study coordinating centre by trained study staff. Staff will receive training on the study protocol, definition of data elements, application of the CCR and elements of the ePCR. A complete list of data points and definitions will be compiled and included in a study manual for reference. The data will be entered electronically. The data entry screens will resemble the paper study forms approved by the Steering Committee (see Appendices 6 and 7). Where possible, the study database will be designed to ensure that each given variable can only be entered in a certain format, thereby limiting the number of errors in data entry. A certain percentage of cases will be entered in duplicate to ensure accuracy. A small percentage of cases (10%) will also be pulled and compared to the source documents to independently verify the accuracy of the data. We will regularly run range and logic checks to previously-entered data to locate and fix any errors or discrepancies in the data set. We will work closely with staff at the participating Base Hospitals and our local EMS Study Champions to locate promptly identify and locate missing data. Queries about particular cases and situations will be flagged for review by the Research Coordinator. If the Research Coordinator is unable to determine the appropriate course of action, the flagged issue will be brought to the attention of the Principal Investigator who will review the issue and advise. Any resulting changes to data definitions will be noted and dated in the study manual.

The study database will be designed and located on servers housed at the Ottawa Hospital Research Institute. All electronic study documents will be saved on network folders with limited access. The network folders are backed up nightly by the Ottawa Hospital Research Network Information Technology team. Paper files will be stored in locked cabinets in locked offices.

